8.4 Adverse Events, Serious Adverse Events, and Other Reportable Safety Events

The definitions of an AE or SAE, as well as the method of recording, evaluating, and assessing causality of AE and SAE and the procedures for completing and transmitting AE, SAE, and other reportable safety event reports can be found in Appendix 3.

Adverse events, SAEs, and other reportable safety events will be reported by the participant (or, when appropriate, by a caregiver, surrogate, or the participant's legally authorized representative).

The investigator and any designees are responsible for detecting, documenting, and reporting events that meet the definition of an AE or SAE as well as other reportable safety events. Investigators need to document if an SAE was associated with a medication error, misuse, or abuse.

Investigators remain responsible for following up AEs, SAEs, and other reportable safety events for outcome according to Section 8.4.3. The investigator, who is a qualified physician, will assess events that meet the definition of an AE or SAE as well as other reportable safety events with respect to seriousness, intensity/toxicity, and causality.

8.4.1 Time Period and Frequency for Collecting AE, SAE, and Other Reportable Safety Event Information

All AEs, SAEs, and other reportable safety events that occur after the participant provides documented informed consent, but before intervention randomization, must be reported by the investigator, if the event causes the participant to be excluded from the study, or is the result of a protocol-specified intervention, including, but not limited to washout or discontinuation of usual therapy, diet, or a procedure.

From the time of intervention randomization through 14 days after cessation of study intervention, all AEs, SAEs, and other reportable safety events must be reported by the investigator.

Additionally, any SAE brought to the attention of an investigator at any time outside the period specified in the previous paragraph must be reported immediately to the Sponsor if the event is considered related to study intervention.

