Investigators are not obligated to actively seek AEs or SAEs or other reportable safety events in former study participants. However, if the investigator learns of any SAE, including a death, at any time after a participant has been discharged from the study, and the investigator considers the event to be reasonably related to the study intervention or study participation, the investigator must promptly notify the Sponsor.

All initial and follow-up AEs, SAEs, and other reportable safety events will be recorded and reported to the Sponsor or designee within the time frames as indicated in Table 3.

Exception: A positive pregnancy test at the time of initial screening is not a reportable event unless the participant has received study intervention.

Type of Event	Reporting Time Period: Consent to Randomization/ Allocation	Reporting TimePeriod:Randomization/AllocationthroughProtocol-specified Follow-up Period	Reporting TimePeriod:After the Protocol-specified Follow-upPeriod	Time Frame to Report Event and Follow-up Information to Sponsor:
NSAE	Report if: - due to protocol- specified intervention - causes exclusion	Report all	Not required	Per data entry guidelines
SAE	Report if: - due to protocol- specified intervention - causes exclusion	Report all	Report if: - drug/vaccine related. (Follow ongoing to outcome)	Within 24 hours of learning of event
Pregnancy/ Lactation Exposure	Report if: - participant has been exposed to any protocol- specified intervention Exception: A positive pregnancy test at the time of initial screening is not a reportable event.	Report all	Report if participant has been exposed to any protocol-specified intervention. Previously reported – Follow to completion/ termination; report outcome	Within 24 hours of learning of event
ECI (require regulatory reporting)	Report if: - due to intervention - causes exclusion	Report - Potential DILI - Require regulatory reporting	Not required	Within 24 hours of learning of event
ECI (do not require regulatory reporting)	Report if: - due to intervention - causes exclusion	Report - non-DILI ECIs and those not requiring regulatory reporting	Not required	Within 5 calendar days of learning of event
Cancer	Report if: - due to intervention - causes exclusion	Report all	Not required	Within 5 calendar days of learning of event (unless serious)
Overdose	Not applicable	Report all	Not required	Within 5 calendar days of learning of event

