Visit 6 is the last visit for the Base Period and the Baseline Visit for the Extension Period. At Visit 6, the participants will complete the Base Period study procedures as scheduled and specified in the SoA and will be given medication diaries and study intervention (MK-5475 or placebo) for the next 12 weeks. Participants in the Phase 3 Cohort Extension Period will receive study intervention every 12 weeks until Final Visit (Section 8.1.8.4).

Participants in both cohorts will record in their medication diary the date and time of investigational product administration as well as any comments related to the administration experience (eg, device issues). Participants will return their diary and used and unused DPIs at every scheduled site visit.

If, at any time during the study, a participant requires a reassessment of study-related clinical, functional, and/or analytical parameters (eg, 6MWD, WHO-FC), an unscheduled visit may occur. In the event of an unscheduled visit, vital signs, AEs, clinical events, and concomitant medication may be assessed, in addition to the procedure(s) that required reassessment.

Clinic in-person visit may be replaced by telephone, video or home visit using a site staff or a nursing service if circumstances do not support an in-person site visit and after consultation with the Sponsor.

8.11.5 Participants Discontinued From Study Intervention but Continuing to be Monitored in the Study

All randomized participants should be followed through completion of the study, regardless of premature discontinuation of study intervention, unless the participant withdraws consent from any study follow-up. Participants who discontinue study intervention during the Phase 2 Cohort Base Period should be followed through completion of that study period (Visit 6).

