In both Phase 2 and Phase 3 Cohorts, if a participant is discontinued from the study intervention at any time before the completion of the study (or study period, for participants who discontinue during the Phase 2 Cohort Base Period), the participant will complete the Discontinuation Visit procedures at the time of discontinuation and a follow-up visit 14 days (+ 2 days) after the last dose of study intervention, as specified in the SoA (Section 1.3). After the discontinuation of study intervention, the site visits should continue to be performed at time points that correspond to each remaining study visit through the end of the study (or study period, for participants who discontinue during the Phase 2 Cohort Base Period).

- If a participant is discontinued from the study intervention at any time during the Base Period of either cohort, the participant will return to the clinic at Week 12 and will complete all Visit 6 procedures, as scheduled and specified in the SoA (Section 1.3).
- At each post-discontinuation visit (other than Week 12 visit), Phase 2 Cohort participants will have their vital signs (pulse rate, BP, temperature, pulse oximetry, and respiratory rate) recorded and a review of AEs/SAEs. Participants who discontinue study intervention during the Extension Period on or before Week 24 will complete the WHO-FC assessment, the 6MWT, and NT-proBNP measurement, as specified in the SoA (Section 1.3), in addition to the review of AEs/SAEs and recording of their vital signs (pulse rate, BP, temperature, pulse oximetry, and respiratory rate).
- At each post-discontinuation visit (other than Week 12 visit), Phase 3 Cohort participants will complete the WHO-FC assessment and 6MWT, as specified in the SoA (Section 1.3), in addition to the review of AEs/SAEs and recording of their vital signs (pulse rate, BP, temperature, pulse oximetry, and respiratory rate).
- Concomitant therapies specifically prohibited (Section 5.2) while the participant was receiving study intervention are no longer prohibited starting 14 days after discontinuation of study intervention.

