9.6.2 Analysis Methods for Safety Analyses

Safety analyses of the Phase 2 Cohort and the Phase 3 Cohort will be performed separately. The analysis methods for safety analyses are the same for both cohorts. The analyses at the end of the Extension Period will include data collected in both the Base and Extension Period of each study cohort.

Safety and tolerability will be assessed by clinical review of all relevant parameters including AEs, laboratory tests, vital signs, PFTs, and ECG measurements. Except where noted otherwise, the same analyses will be performed at the end of the Base Period and at the end of the Extension Period.

The Treatment Period will include all data from randomization up to 14 days after the last dose of study medication. All safety endpoints will be analyzed for the time frame consisting of the treatment period + 14-day post-treatment follow-up, except SAEs. For SAEs, the analysis will include all post-treatment follow-up.

AEs will be coded using the standard MedDRA and grouped according to SOC.

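### The SAE analysis covers all post-treatment follow-up, but the reporting rules conflict on whether unrelated SAEs more than 14 days after stopping must be reported

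*Combined protocol and SAP*

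**What the plan says.** On analysis, Section 9.6.2 states: "All safety endpoints will be analyzed for the time frame consisting of the treatment period + 14-day post-treatment follow-up, except SAEs". For the exception it adds: "For SAEs, the analysis will include all post-treatment follow-up". No upper limit and no causality restriction are attached.

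On reporting, the text of Section 8.4.1 sets the full-reporting period from randomization "through 14 days after cessation of study intervention, all AEs, SAEs, and other reportable safety events must be reported by the investigator". An SAE outside that period "must be reported immediately to the Sponsor if the event is considered related to study intervention". Table 3 in the same section draws the line differently. It asks for all SAEs up to the end of a protocol-specified follow-up period, which it does not define; after that the SAE entry is "Report if: - drug/vaccine related. (Follow ongoing to outcome".

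On follow-up, Section 8.11.5 states: "All randomized participants should be followed through completion of the study, regardless of premature discontinuation of study intervention". The exception is participants who stop during the Phase 2 Base Period, who are followed to Visit 6. At each later Phase 3 visit other than Week 12, functional class and walk test are done "in addition to the review of AEs/SAEs and recording of their vital signs". Phase 2 participants also have AEs and SAEs reviewed at these visits. Section 8.3.9 has AEs recorded throughout the study and its follow-up.

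**The concern.** The analysis window is wider than the window in which the text of Section 8.4.1 makes SAE reporting mandatory whatever the cause. Beyond day 14, two sites with the same event could act differently. One follows Section 8.4.1 and reports only what it judges related; the other treats the Section 8.11.5 review as a duty to report everything. Both could claim to follow the protocol.

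Section 9.6.2.1 plans the number and percentage of participants with at least one SAE, with between-group differences and 95% confidence intervals. The footnote to Table 7 removes the intervals only for the Phase 2 Extension, so the Phase 3 Extension analysis keeps them. If late SAEs are captured by causality opinion, that table under-counts, and does so unequally if early stopping differs by arm.

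There is also a consistency problem. The adjudication committee (Section 10.1.4.4) reviews deaths and PAH-related hospitalizations, including those after discontinuation. Both meet the SAE definition in Section 10.3.3, and Section 8.4.6 exempts no disease-related events. A hospitalization judged unrelated after day 14 could count as clinical worsening yet be absent from the SAE table.

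**Working it through.** The plan gives no figure for this point, so there is nothing to reproduce. The check is a comparison of rules, then a bound on the exposed time, then an illustration on stated assumptions.

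**1. Rules for an unrelated SAE more than 14 days after the last dose, participant still attending**

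| Place | What it implies |
|---|---|
| 8.4.1, text | Not required |
| Table 3 | Required if the undefined follow-up period runs to the last visit; not required if it ends at the 14-day follow-up visit |
| 8.11.5 | Reviewed at each visit; duty to report not stated |
| 8.3.9 | AEs recorded throughout the study; no reporting rule for this case |
| 7.1 | Certain clinical event data collected to the last scheduled follow-up; SAEs not named |
| 9.6.2 | Included in the analysis |

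The last row depends on events that the first row does not require, and the rows between do not settle the difference.

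**2. Who is exposed, and for how long**

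Completers have their last contact about 14 days after the last dose (Section 8.11.7), so the wider window adds almost nothing for them. It concerns participants who stop early and stay in follow-up.

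- Base Period: dosing is planned for 84 days. A participant who stops on Day 1 has at most 84 − 14 = 70 days beyond the full-reporting window, to Week 12.
- Phase 3 Extension: up to 5 years, so the exposed time can run to years.

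**3. Illustration only**

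None of these inputs is in the documents: a share q = 10% of an arm stops and stays in follow-up; SAE rate λ = 0.2 to 0.5 per year; share judged related r = 5% to 20%; time beyond day 14 of T years. If every site followed only the text of 8.4.1, the shortfall in the percentage with an SAE would be

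q × {[1 − exp(−λT)] − [1 − exp(−λrT)]}.

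- T = 35 days (half of 70): 0.2 to 0.4 percentage points.
- T = 1 year: low end 0.10 × (0.181 − 0.039) = 1.4 points; high end 0.10 × (0.393 − 0.025) = 3.7 points.
- T = 3 years: low end 0.10 × (0.451 − 0.113) = 3.4 points; high end 0.10 × (0.777 − 0.072) = 7.0 points.

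If 15% stopped in one arm and 5% in the other (λ = 0.3, r = 10%), the between-arm distortion would be 0.10 × (0.259 − 0.030) = 2.3 points at 1 year and 0.10 × (0.593 − 0.086) = 5.1 points at 3 years.

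These values overstate the shortfall on their own assumptions, because the formula does not remove participants already counted for an SAE within the 14-day window. If the Section 8.11.5 reviews feed the database in full, the shortfall among those still attending is close to zero.

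**The case against.** The strongest reply is that the protocol, read as a whole, already collects everything. Table 3 is the table to which Section 8.4.1 refers for reporting time frames. If its follow-up period is the one in Section 8.11.5, all SAEs are reportable to study completion. The release from active searching covers only people who have left: "Investigators are not obligated to actively seek AEs or SAEs or other reportable safety events in former study participants". Section 8.11.6 brings Phase 3 participants who stopped early back to the Final Visit for collection of clinical events. Adjudication gives deaths and PAH-related hospitalizations a second route that does not depend on drug causality. The schedule of activities (Section 1.3) is not in the text available here and might settle the matter.

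Much of this stands. A reader might infer that SAE incidence will certainly mix full and selective capture. The documents do not support that, because a site following Section 8.11.5 and the wider reading of Table 3 would report everything. The reply does not remove the conflict, however. Table 3 does not define its period, and because those who stop have a follow-up visit 14 days after the last dose, a site could fairly read the period as ending there.

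A reader might also infer a number of affected participants by applying the 10% drop-out in Section 9.9.1 to 143 per arm. That is not supported either. There, drop-out means Week 12 data that must be imputed (30 m × 0.9 = 27 m). Participants who stop but keep attending supply their own Week 12 values under the treatment-policy strategy. The 10% is therefore not a count of people in long off-drug follow-up.

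Finally, Section 9.6.2.1 describes the intervals as descriptive and not a formal assessment of significance. No efficacy test, power or alpha is affected. That limits the consequence and is accepted.

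**Conclusion.** The conflict between the SAE analysis window and the text of the reporting rule is real and unreconciled. What follows from it is possible rather than certain: for participants who stop study intervention but remain in follow-up, SAE counts may be incomplete and filtered by causality, depending on which rule a site applies.

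The size is unknown. It depends on how many stop early and stay in follow-up, how long they are followed, the SAE rate, the share judged related and site practice, and the documents give none of these for the period concerned. The Base Period analyses have little exposure. The Phase 3 Extension analysis is where it could matter, because follow-up is long and between-group intervals are kept. Unequal stopping by arm would be needed for an appreciable between-arm distortion; the plan does not predict it, since it assumes about 10% drop-out in each group to Week 12. The point is worth correcting because the remedy is cheap, not because a known bias has been shown.

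**What to change.** - **Sections 8.4.1 and Table 3:** state that for participants who stop study intervention but remain in follow-up, all SAEs, regardless of causality, are reported through the last study contact. Define Table 3's follow-up period to match, and refer to this rule in Section 8.11.5.
- **Section 9.6.2:** summarise SAEs to 14 days after the last dose and, separately, over all follow-up.
- **If collection is not extended:** limit the between-group SAE summary to the window with full reporting and list later (related) SAEs separately, so that they are not lost.
- **At the same time:** clarify the cut-off in Section 9.6.2. It defines the Treatment Period as already running to 14 days after the last dose and then adds a 14-day follow-up, so the limit can be read as 14 or 28 days.

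The cost is protocol and SAP wording plus a few more SAE reports. The visits and the SAE review at them already exist.

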9.6.2.1 Overall Safety Assessment

The overall safety evaluation will include a summary by treatment group of the number and percentage of participants with at least one AE, drug-related AE, SAE, and drug-related SAE, as well as who discontinued from study intervention due to an AE and who had an AE resulting in death. Point estimates and 95% CIs for the differences between treatment groups in the percentages of participants with these events will be provided.

The number and percentage of participants with specific AEs will also be provided. Point estimates and 95% CIs for the differences between treatment groups in the percentages of participants with specific AEs will be provided for AEs that occur in at least 4 participants in any treatment group. This threshold for the numbers of events was chosen because the 95% CI for the between-group difference in percent incidence will always include zero when fewer participants per group have events and thus would add little to the interpretation of potentially meaningful differences.

Point estimates and 95% CIs will be provided for the percentage of participants with safety parameters that meet predefined limits of change based on the same criteria used above for the specific AEs.

CIs for between-treatment group differences will be provided using the Miettinen and Nurminen (M&N) method [Miettinen, O. and Nurminen, M. 1985]. These CIs will not be adjusted for multiplicity and should be regarded only as helpful descriptive measures for the review of the safety profile and not as a formal method for assessing statistical significance of between-group differences. Rainfall plots with point estimates and 95% CIs will be displayed for AEs that occur in at least 4 participants in any treatment group.

Assessment of Safety Topics of Interest

Safety topics of interest include AEs of symptomatic hypotension, pulmonary hemorrhage, and hemoptysis. The safety topics of special interest will be summarized by treatment group of the number and percentage of participants. Point estimates and 95% CIs for between-group differences will be provided based on the criteria described above for specific AEs.

A summary of the analysis strategy for safety parameters is provided in Table 7.

Analysis Part	Safety Endpoint	Descriptive Statistics	95% Between- group CIª	Graphical Display ^a
Overall Safety Assessment	Any AE	Х	Х	
	Any serious AE	Х	Х	
	Any drug-related AE	Х	Х	
	Any serious and drug-related AE	Х	Х	
	Discontinuation due to AE	Х	Х	
	Death	Х	Х	
pan gro Sp	SOCs, PDLCs (incidence ≥4 of participants in any treatment groups)	Х	Х	
	Specific AEs (incidence ≥4 of participants in any treatment groups)	Х	Х	Х
	Specific AEs, SOCs, PDLCs (incidence <4 of participants in any treatment groups)	Х		
	Change from Baseline results (laboratory tests, ECGs, vital signs)	Х		
Safety Topics of Special Interest	Symptomatic hypotension Pulmonary hemorrhage Hemoptysis	Х	Х	Х

 Table 7
 Analysis Strategy for Safety Parameters

AE=adverse event; CI=confidence interval; ECGs=electrocardiograms; PDLC=predefined limit of change; SOC=system organ class; X=results will be provided.

^a 95% between-group CI and graphical display will not be provided for the analysis of the Phase 2 Cohort Extension Period.

[figure not shown]
9.6.3 Summaries of Demographic and Baseline Characteristics

The comparability of the treatment groups for each relevant demographic and baseline characteristic will be assessed separately for each cohort by the use of tables and/or graphs. No statistical hypothesis tests will be performed on these characteristics. The number and percentage of participants screened and randomized and the primary reasons for screening failure and discontinuation will be displayed. Demographic variables (eg, age), baseline characteristics, primary and secondary diagnoses, and prior and concomitant therapies will be summarized by treatment either by descriptive statistics or categorical tables.

For analysis purposes, the baseline assessment is considered the one closest to but before or on the day of randomization (Day 1).

9.7 Interim Analyses

Analyses of data to be performed while the study is in progress are described below.

The O'Brien–Fleming alpha-spending function [Lan, K. K. G. and DeMets, D. L. 1983] will be used for the efficacy IA to assess the superiority of MK-5475 versus placebo. The spending function can be expressed as

$$\alpha(t) = 2 - 2\Phi\left(\frac{Z_{\alpha/2}}{\sqrt{t}}\right)$$

where 't' denotes the percentage of information included at the IA, and ' Φ ' denotes the standard normal cumulative distribution function.

[figure not shown]
With this alpha spending approach, the cumulative significance level will be approximately (one-sided) at the IA and **Control** at the final analysis of the Phase 2 Cohort Base Period, respectively. This testing approach controls the one-sided alpha between the efficacy IA and final analysis at 0.025. The operating characteristics for the interim efficacy analysis are shown in Table 8.

Table 8Power to Demonstrate Superiority of MK-5475 vs placebo on the Primary
Endpoint of % Change in PVR in Phase 2 Cohort Base Period at the Interim Analysis

Analysis timepoint	Cumulative a Spent	Pow	er (%) foi	· Various]	Frue Effect	t Sizes
	(one-sided)	-30%	-35%	-40%	-45%	-50%
	CCI	59.5	75.0	86.7	93.9	97.6

IA=interim analysis; PVR=pulmonary vascular resistance.

Study enrollment will not be paused while the IA is being conducted. Blinding to treatment assignment will be maintained at all investigational sites. Participant-level unblinding will be restricted to an internal unblinded statistician and a scientific programmer performing the IA. Treatment-level results and/or participant-level data from the IA will be provided by the unblinded statistician to the eDMC. Limited additional Sponsor personnel may be unblinded to the treatment-level results of the IA, if required, to act on the recommendations of the eDMC. The processes by which recommendations and decisions are reached and communicated will be documented in the DMC charter. Before final study unblinding, individuals who have been unblinded at any level will not be involved in any discussions regarding modifications to the protocol, statistical methods, identification of protocol deviations, or data validation efforts after the IA. The results of the IA will not be shared with the investigators before completion of the Phase 2 Cohort.

Phase 2 Cohort Base Period

If the IA is cancelled, at the end of the Phase 2 Cohort Base Period, selected members of the Sponsor study team and management will be unblinded to comprehensive results from the Phase 2 Cohort Base Period to evaluate the efficacy and safety profile of MK-5475 for selecting a dose for the Phase 3 Cohort. The MCP-Mod method [Center for Drug Evaluation and Research 2015] may be used to support the finding of a suitable dose for Phase 3 Cohort. Details will be described in the sSAP. This study may stop if analysis of the data collected at the end of the Phase 2 Cohort Base Period shows that none of the MK-5475 doses has a desirable efficacy and safety profile.

Phase 3 Cohort Base Period

The analysis at the end of Phase 3 Cohort Base Period represents the final analysis for Phase 3 Cohort Base Period. At the end of the Phase 3 Cohort Base Period, selected members of the Sponsor study team and management will be unblinded to comprehensive Base Period results from the Phase 3 Cohort, for preparing a CSR and regulatory submissions. For the Extension Period of Phase 3 Cohort, a separate blinded Sponsor study team will monitor the ongoing study. Individuals directly involved with study conduct will not be unblinded.

Data Monitoring Committee

To supplement the routine trial monitoring outlined in this study, an external DMC will monitor the interim data. The DMC will not be involved in the dose selection decision. More details are described in Section 10.1.4.3.

